### **5.2.3            Prior and Concomitant Therapy**

#### **5.2.3.1        Prior Therapy**

Any medication or vaccine (including over-the-counter or prescription medicines, vitamins and/or herbal supplements) that the subject has received within 30 days prior to Baseline, is receiving at the time of enrollment, or receives during the study, must be recorded along with the reason for use, date(s) of administration including start and end dates, and dosage information including dose, route and frequency in source documents and the eCRFs. The reason for use, date(s) of administration (including start and end dates), and dosage information (including dose and frequency) must be recorded.

The history of previous use (including the duration of therapy, the highest known dose taken, reason for use and reason[s] for termination of treatment) of the immunomodulator, anti-TNF and/or biologic agents will be recorded in the appropriate eCRF. Subjects who have not been exposed to an anti-TNF will have their immunosuppressants recorded beyond the past 90 days.

The AbbVie study designated physician identified in Section [6.1.5](#) should be contacted if there are any questions regarding concomitant or prior therapy(ies).

#### **5.2.3.2        Concomitant Therapy**

Subjects who enter the study on aminosalicylates and/or MTX must remain on stable dose of this therapy for the entire study period.

Subjects who enter the study on Crohn's disease related antibiotics must remain on stable doses of this medication for at least 14 days prior to Baseline. Change in dose of Crohn's disease related antibiotics during the study will not be allowed for the 16-week induction

---

period, except in cases of treatment related toxicity or concerns about development of antibiotic resistance.

Subjects who enter the study on oral corticosteroids are not allowed to change the corticosteroid dose during the first 2 weeks of the treatment period. At Week 2, subjects who are taking corticosteroid therapy at Baseline must have their corticosteroid therapy tapered according to a tapering schedule specified below and in Section [5.3.1.1](#).

A proposed schedule to taper prednisone dose starts with a weekly decrease by 5 mg/day prednisone (or equivalent) for doses > 10 mg/day of prednisone (or equivalent) until a 10 mg/day (or equivalent) dose is reached, then a weekly decrease by 2.5 mg/day (or equivalent) until discontinuation.

A proposed schedule to taper budesonide dose starts with a weekly decrease by 3 mg budesonide until discontinuation.

If a subject should experience an inadequate response during the corticosteroid taper, the subject may have their corticosteroid dose increased per the investigator's discretion up to and beyond the dose used at Baseline. Subjects in whom the maximum steroid dose exceeds the dose used at Baseline will be considered non-responders and will be censored for efficacy assessments from that point forward through the end of the study. These subjects will continue to be evaluated in the safety population.

Use of inhaled or topical dermatologic corticosteroids is not restricted.

Subjects who enter the study on probiotics may continue this therapy provided doses remain stable from Baseline throughout the duration of the study.

Setons are authorized as concomitant therapy in subjects with perianal fistulas and should be documented in the CRF under concomitant medications.

The AbbVie Study Designated Physician identified in Section [6.1.5](#) should be contacted if there are any questions regarding concomitant or prior therapy(ies).

### **5.2.3.3 Prohibited Therapy**

The following are prohibited medications during the study:

- All biologic therapy with a potential therapeutic impact on the disease being studied including but not limited to the following:
  - Etanercept (Enbrel®);
  - Abatacept (Orencia®);
  - Anakinra (Kineret®);
  - Rituximab (Rituxan®);
  - Natalizumab (Tysabri®);
  - Tocilizumab (Actemra®);
  - Efalizumab (Raptiva®);
  - Ustekinumab (Stelara®);
  - Belimumab (Benlysta®);
  - Golimumab (Simponi®);
  - Vedolizumab (Entyvio®);
  - Infliximab (Remicade®);
  - Certolizumab pegol (Cimzia®).
- JAK inhibitors (e.g., tofacitinib [Xeljanz®])
- NSAIDs (except topical NSAIDs and the use of low dose aspirin for CV protection).
- Live vaccines are NOT allowed within 1 month prior to Screening and during the study. Examples of live vaccines include but are not limited to the following:
  - monovalent live attenuated influenza A (H1N1) (intranasal)
  - seasonal trivalent live attenuated influenza (intranasal)
  - herpes zoster, rotavirus
  - varicella (chicken pox)
  - measles-mumps-rubella (MMR) or measles mumps rubella varicella (MMRV)

- oral polio vaccine (OPV)
  - smallpox
  - yellow fever
  - Bacille Calmette-Guérin (BCG)
  - typhoid
- Rectal therapy with any therapeutic enemas or suppositories, with the exception of those required for endoscopy, is prohibited within 7 days prior to Screening endoscopy, during the remainder of the Screening Period and during the study.
- Intravenous corticosteroid use is prohibited within 14 days prior to Screening or during the Screening Period and during the study.
- Cyclosporine, tacrolimus, or mycophenolate mofetil use is prohibited within 30 days prior to Baseline and during the study.
- Azathioprine or 6-mercaptopurine (6-MP) use is prohibited within 10 days prior to Baseline and during the study.
- Investigational drugs of a chemical or biologic nature are prohibited within 30 days, or 5 half-lives (whichever is longer) of the drug prior to the Baseline and during the study.
- Use of strong CYP3A inhibitors (e.g., clarithromycin, conivaptan, itraconazole, ketoconazole, posaconazole, telithromycin, voriconazole, grapefruit juice) or strong CYP3A inducers (e.g., rifampin, carbamazepine, phenytoin, St. John's wort) should be avoided from the Screening visit through the end of the study.

Note: Infliximab (Remicade®), Certolizumab (Cimzia®), Adalimumab (HUMIRA®), Vedolizumab (Entyvio®), Natalizumab (Tysabri®) are prohibited within 8 weeks prior to Baseline and during the study. Ustekinumab (Stelara®) is prohibited within 12 weeks prior to Baseline of during the study.

The AbbVie study designated physician identified in Section 6.1.5 should be contacted if there are any questions regarding prohibited therapy.

## 5.2.4 Contraceptive Recommendations

### Contraception Recommendation for Females

A woman who is postmenopausal or permanently surgically sterile (bilateral oophorectomy, bilateral salpingectomy or hysterectomy) is not considered to be a woman of childbearing potential and is not required to follow contraception recommendations.

Postmenopausal is defined as:

- Age  $\geq$  55 years with no menses for 12 or more months without an alternative medical cause; or
- Age  $<$  55 years with no menses for 12 or more months without an alternative medical cause AND an FSH level  $>$  40 mIU/mL.

A woman who does not meet the definition of postmenopausal or permanently surgically sterile is considered a woman of childbearing potential and is required to practice at least one of the following highly effective method of birth control, on Study Day 1 (or earlier) through at least 30 days after the last dose of study drug.

- Combined (estrogen and progestogen containing) hormonal contraception (oral, intravaginal, transdermal) associated with the inhibition of ovulation, initiated at least 1 month prior to Study Day 1.
- Progestogen-only hormonal contraception (oral, injectable, implantable) associated with inhibition of ovulation, initiated at least 1 month prior to Study Day 1.
- Bilateral tubal ligation.
- Vasectomized partner(s), provided the vasectomized partner has received medical assessment of the surgical success and is the sole sexual partner of the WOCBP trial participant.
- Intrauterine device (IUD).
- Intrauterine hormone-releasing system (IUS).
- True abstinence: Refraining from heterosexual intercourse when this is in line with the preferred and usual lifestyle of the subject (periodic abstinence)

---

[e.g., calendar, ovulation, symptothermal, post-ovulation methods] and withdrawal are not acceptable)

If required per local practices, male or female condom with or without spermicide OR cap, diaphragm or sponge with spermicide should be used in addition to one of the highly effective birth control methods listed above (excluding true abstinence).

It is important to note that contraception requirements described above are specifically intended to prevent pregnancy during exposure to the investigational therapy ABT-494. The concomitant methotrexate (MTX) that may have been prescribed per standard of care prior to study entry and are allowed to be continued during the study. Contraception should continue while the subject is on the concomitant MTX and that duration of contraception after discontinuation of the MTX should be based on the local label.

#### **Contraception Recommendation for Males**

For a male subject has a female partner who is postmenopausal or permanently sterile (bilateral oophorectomy, bilateral salpingectomy or hysterectomy), no contraception is required.

A male subject who is sexually active with female partner(s) of childbearing potential, must agree from Study Day 1 through 30 days after the last dose of study drug to practice contraception with:

- Condom use and female partner(s) using at least one of the contraceptive measures as defined in the protocol for female study subjects of childbearing potential.

OR

- True abstinence: Refraining from heterosexual intercourse-when this is in line with the preferred and usual lifestyle of the subject. (Note: Periodic abstinence [e.g., calendar, ovulation, symptothermal, post-ovulation methods] and withdrawal are not acceptable).

Additionally, male subject agrees not to donate sperm from Study Day 1 through 30 days after the last dose of study drug.

Male subjects are responsible for informing his partner(s) of the risk of becoming pregnant and reporting any pregnancy to the Investigator. If a pregnancy occurs, a partner authorization form requesting pregnancy outcome information will be requested from the pregnant partner.

It is important to note that contraception and sperm donation recommendations described above are specifically intended to prevent pregnancy during and after exposure to the investigational therapy ABT-494. The concomitant methotrexate (MTX) that may have been prescribed per standard of care prior to study entry and are allowed to be continued during the study. Contraception should continue while the subject is on the concomitant MTX and that duration of contraception and the requirement not to donate sperm after discontinuation of the MTX should be based on the local label.

### **5.3 Efficacy and Safety Assessments/Variables**

Study procedures will be performed as summarized in Section 5.3.1.1. All subjects must meet the study selection criteria outlined in Section 5.2.1 and Section 5.2.2 in order to be randomized in to the study.

#### **5.3.1 Efficacy and Safety Measurements Assessed and Flow Chart**

**Table 1.** Study Activities

Activity	Screening a	Baseline (Week 0)	Wk 2	Wk 4	Wk 8	Wk 12	Wk 16	Wk 20	Wk 28	Wk 36	Wk 44	Wk 52	Early Termination (ET) Visit	Unscheduled Visit	30-Day Follow-Up Visit
Informed Consent	X														
Inclusion/Exclusion b	X	X													
Medical/Surgical History b	X	X													
Prior and Concomitant Medications b	X	X	X	X	X	X	X	X	X	X	X	X	X	X	
Physical Exam c	X	X	X	X	X	X	X	X	X	X	X	X	X	X	
Endoscopy d	X					X	X					X	X		
Biopsy e	X					X	X					X	X		
SES-CD		X				X	X					X	X		
Vital Signs f	X	X	X	X	X	X	X	X	X	X	X	X	X	X	X
12-Lead ECG g	X													X v	
Chest X-Ray h	X													X v	
PPD Skin Test or QuantiFERON TB Gold Test i	X														
Latent TB Risk Factor Questionnaire	X														
Blood Chemistry and Hematology	X w	X	X	X	X	X	X	X	X	X	X	X	X	X	X

**Table 1. Study Activities (Continued)**

Activity	Screening a	Baseline (Week 0)	Wk 2	Wk 4	Wk 8	Wk 12	Wk 16	Wk 20	Wk 28	Wk 36	Wk 44	Wk 52	Early Termination (ET) Visit	Unscheduled Visit	30-Day Follow-Up Visit
Urinalysis j	X	X	X	X	X	X	X	X	X	X	X	X	X	X	X
Pregnancy Test k	X	X	X	X	X	X	X	X	X	X	X	X	X		X
hsCRP	X	X	X	X	X	X	X	X	X	X	X	X	X	X	X
HBV and HCV Screening l	X														
ABT-494 Concentration m			X	X	X	X	X	X	X	X	X	X	X		
Pharmacodynamic biomarkers		X			X		X						X	X	
C. difficile toxin	X														
Stool Sample (fecal calprotectin) n,o	X			X			X		X			X	X		
Bristol Stool Chart	X			X			X		X			X	X		
Corticosteroid Taper q			X												
Crohn's Disease Activity Index (CDAI)		X	X	X	X	X	X	X	X	X	X	X	X	X	
Inflammatory Bowel Disease Questionnaire (IBDQ)		X			X		X					X	X		

**Table 1. Study Activities (Continued)**

Activity	Screening a	Baseline (Week 0)	Wk 2	Wk 4	Wk 8	Wk 12	Wk 16	Wk 20	Wk 28	Wk 36	Wk 44	Wk 52	Early Termination (ET) Visit	Unscheduled Visit	30-Day Follow-Up Visit
European Quality of Life 5 Dimensions (EQ-5D)		X			X		X						X	X	
Work Productivity and Impairment Questionnaire (WPAI)		X			X		X						X	X	
Abdominal Pain Rating Scale (0 – 10 Scale)		X				X	X								
Monitor Adverse Events r	X	X	X	X	X	X	X	X	X	X	X	X	X	X	X
Study Drug Dispensing/Administration		X	X	X	X	X	X	X	X	X	X				
Dispense Subject Diary	X														
Subject Diary Review		X	X	X	X	X	X	X	X	X	X	X	X	X	

**Table 1. Study Activities (Continued)**

Activity	Screening a	Baseline (Week 0)	Wk 2	Wk 4	Wk 8	Wk 12	Wk 16	Wk 20	Wk 28	Wk 36	Wk 44	Wk 52	Early Termination (ET) Visit	Unscheduled Visit	30-Day Follow-Up Visit
Additional Samples Collection (Optional)															
Pharmacogenetic s		X													
Serologic markers t		X					X								
mRNA t		X					X								
Biopsy for gene expression u	X					X	X								

Wk = Week

- The Screening period will be a minimum of 7 days but no more than 35 days. Baseline Visit date will serve as the reference for all subsequent visits. A  $\pm$  3-day window is permitted around scheduled study visits.
- Update inclusion/exclusion, prior and concomitant therapy, and medical/surgical history information to assure subject eligibility.
- Physical examination performed at Screening, Baseline, Week 16 and Week 52/Early Termination Visits are full physical examinations which must include an assessment of extra-intestinal manifestations (EIMs) and a count of the number of cutaneous fistulas. Physical examinations and those performed at all other visits are symptom based but must include a count of the number of cutaneous fistulas.
- Colonoscopy at/during the screening period or within 15 days of the Screening Visit will be used to calculate the SES-CD score at Baseline. Subject will be randomly assigned at Baseline to have endoscopy performed at Week 12 or Week 16.
- Biopsy may be done when performing the endoscopy. Biopsy to confirm CD diagnosis may be done when performing the endoscopy if appropriate documentation for confirmation of the diagnosis does not exist. Biopsies to rule out dysplasia and colon cancer may be taken at the investigator's discretion.
- Blood pressure, pulse rate, temperature, respiratory rate and weight should be performed before blood draws are performed. Height will be measured at Screening only (with shoes off and then adding 1 inch or 2.5 cm).
- Subjects with normal ECG within 90 days of Screening would not require a repeat ECG, if documentation is available. Subjects can have a repeat ECG at any time during the study as warranted based on the opinion of the Investigator.

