### Screening Period

Within 35 days prior to the Baseline Visit, subjects will receive a full explanation of the study design and study procedures, provide a written informed consent, and undergo the screening procedures as outlined in [Table 1](#).

An e-diary will be dispensed and training will be provided to the subject at the Screening Visit.

Laboratory tests performed during the Screening period can be repeated in case the abnormalities are considered to be transient by the investigator.

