**CDAI**

A CDAI will be calculated from a subject diary, physical exam, and appropriate laboratory values at all study visits beginning at Screening. The Screening Period will be a minimum of 7 days but will not exceed 35 days. The CDAI calculated during Screening will serve as the Baseline CDAI.

For calculation of CDAI scores, beginning with the Week 2 through Week 52, the CDAI scores must be calculated using a hematocrit value from the preceding visit laboratory work.

CDAI at Visit	Hematocrit Value Utilized
Week 2	Baseline
Week 4	Week 2
Week 8	Week 4
Week 12	Week 8
Week 16	Week 12
Week 20	Week 16
Week 28	Week 20
Week 36	Week 28
Week 44	Week 36
Week 52	Week 44

For calculating CDAI, to answer questions one (1) through three (3), entries from the 7 days prior to the day of study visit should be used as recorded by the subject from the diary.

Diary entries should not be included in the 7 days evaluated prior to the visit if: (1) the day the subject received medication for bowel preparation prior to endoscopy, (2) the day the subject underwent an endoscopy, and (3) 2 days following the endoscopy. Earlier diary entries will be used accordingly in order to provide the most recent data for 7 days prior to the respective study visit.

For the CDAI questions regarding presence of anal fistulas and other fistulas, all fistulas detectable on physical examination (draining and non-draining) should be captured on the CDAI and calculated into the CDAI score.

When completing question five (5) ("Taking Lomotil/Imodium/Loperamide/opiates for diarrhea, 0 = no, 1 = yes") on the CDAI, "no" should be answered if a subject is taking an opiate(s) solely for pain.

For question seven (7), hematocrit results from central laboratory will be used for the CDAI calculation. If the hematocrit value contains more than one decimal point, the rounding will be allowed to the tenths decimal (e.g., Hematocrit value 33.44 will be captured as 33.4, Hematocrit value of 33.45 will be captured as 33.5). The Hematocrit values either prior to completing the calculation or at the subtotal box 7 of the CDAI should not be rounded to a whole number.

The height obtained at Screening should be used when selecting the standard weight in [Appendix E](#), and this standard weight should be used for calculating every CDAI throughout subject participation in the study.

Standard height is calculated by using the height obtained at Screening (without shoes) plus one inch.

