If a subject has less than 4 days of diary data, the total CDAI score will not be calculated and will be considered missing.

Same rule will be applied to average daily stool frequency and average daily abdominal pain.

Bristol Stool Chart

Up to 14 days of diary entries will be evaluated from the ePRO tool for the Bristol Stool Chart calculation. These assessments on the day of endoscopy procedure, the day before endoscopy procedure (due to preparation medications), and 2 days after endoscopy procedure are excluded. The 7 most recent non-missing assessments will be used for the

analysis. The Bristol Stool Chart is calculated as the number of days the subjects with Type 6 or Type 7 divided by the total number days with non-missing assessments, rounded to two decimal.

If a subject has less than 4 days of diary data, the Bristol Stool Chart will not be calculated and will be considered missing.

If a subject achieved reduction from Baseline $\geq 50\%$, this subject will be classified as Responder.

SES-CD Scoring

All colonoscopies shall be performed and recorded in video format. To be eligible for the study, the screening colonoscopy may be performed during the Screening Period (or up to 45 days before the Baseline visit if Amendment 2 is in place at the site). Colonoscopies will also be performed at the Week 12 or 16 visit. Investigators shall provide their SES-CD score assessment on the SES-CD score sheet for the baseline and Week 12 or 16 visits. The investigator SES-CD scores are to be entered in the appropriate eCRF, however neither the Investigator's Baseline nor Week 12 or 16 SES-CD scores will be used for the study's efficacy analyses.

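### The 7-day Screening minimum does not guarantee 4 usable Baseline diary days when the ileocolonoscopy is done during Screening

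*Protocol*

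**What the plan says.** - **Length of Screening.** Protocol Table 1, footnote a: "The Screening period will be a minimum of 7 days but no more than 35 days". The CDAI part of Section 5.3.1.1 repeats both limits.
- **Start of the diary.** Protocol Section 5.1, Screening Period: "An e-diary will be dispensed and training will be provided to the subject at the Screening Visit".
- **Source of Baseline.** Protocol Section 5.3.1.1, CDAI: "The CDAI calculated during Screening will serve as the Baseline CDAI". For the three diary questions, "entries from the 7 days prior to the day of study visit should be used as recorded by the subject from the diary".
- **Days that do not count.** The same section removes "the day the subject received medication for bowel preparation prior to endoscopy", and also "the day the subject underwent an endoscopy, and (3) 2 days following the endoscopy". Older entries are to be used in their place. Protocol Sections 8.1.3 and 8.1.6.1.1 apply the same exclusions to SF and AP.
- **Minimum data.** Section 6.0 of both the Induction and the Extension SAP: "If a subject has less than 4 days of diary data, the total CDAI score will not be calculated and will be considered missing". Both extend the rule to average daily SF and AP, and both limit the look-back to 14 days. The protocol has the 4-day minimum for SF and AP in its synopsis and in Sections 8.1.3 and 8.1.6.1.1, with Weeks 12 and 16 as its examples.
- **Use of the scores.** Inclusion 3 is a threshold on SF or AP, and inclusion 4 is the CDAI range 220 to 450 (Protocol Section 5.2.1). Clinical remission, a co-primary endpoint, requires SF and AP to be no worse than Baseline (Section 5.3.3).

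**The concern.** Replacing excluded days with older entries works at Weeks 12, 16 and 52, because the diary runs throughout the study. It cannot work at Baseline, because there is no diary before the Screening Visit. A schedule that meets Table 1 exactly can therefore leave fewer usable days than the analysis rules accept.

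Two things are at stake. First, eligibility on inclusion 3 and 4 would rest on too few days, or on a score that the analysis later discards. Second, if Baseline SF or AP is missing, the comparison with Baseline inside clinical remission cannot be made. Under non-responder imputation (NRI) the subject is then a failure whatever happened on treatment. Clinical response, a percentage reduction from Baseline, has the same problem. The SAPs say what to do when Baseline SES-CD items are missing, but give no such rule for SF, AP or CDAI.

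**Working it through.** **Inputs.** Screening of at least 7 and at most 35 days (Table 1, footnote a); diary from the Screening Visit (Section 5.1); excluded days as listed in Section 5.3.1.1; at least 4 usable days and up to 7 used (SAP Section 6.0).

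**Assumptions not in the documents.** One preparation day, and a first diary entry on the Screening day itself. Both are varied below.

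**Formula.** Number the diary days 1 to D, with the Baseline Visit on day D + 1. With p preparation days and endoscopy on day s, days s − p to s + 2 are excluded. If all of these fall inside the diary period, usable days = D − (p + 3).

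**At the 7-day minimum** (D = 7, p = 1): 7 − (1 + 3) = 3, against a required 4. By endoscopy day, with the preparation day also inside Screening:

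| Endoscopy on diary day | Days before Baseline | Diary days excluded | Usable days |
|---|---|---|---|
| 2 | 6 | 1–4 | 3 |
| 3 | 5 | 2–5 | 3 |
| 4 | 4 | 3–6 | 3 |
| 5 | 3 | 4–7 | 3 |
| 6 | 2 | 5–7 | 4 |
| 7 | 1 | 6–7 | 5 |

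Four of the six placements fall below 4 usable days, and none gives 7.

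**Endoscopy on or before the Screening Visit** (D = 7): on the day itself, prepared the day before, 4 usable days; one day earlier, 5; two days earlier, 6; three or more days earlier, 7, so nothing is lost.

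**Length that guarantees enough days, whatever the endoscopy day.** For 4 usable days: 4 + 4 = 8 diary days. For 7 usable days: 7 + 4 = 11 diary days.

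**Varying the two assumptions:**

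| Preparation days | First entry | Placements below 4 at D = 7 | Days needed for 4 usable | Days needed for 7 usable |
|---|---|---|---|---|
| 1 | Screening day | 4 of 6 | 8 | 11 |
| 2 | Screening day | 4 of 5 | 9 | 12 |
| 1 | day after | 5 of 6 | 9 | 12 |
| 2 | day after | 5 of 5 | 10 | 13 |

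All of these lengths fit within the 35-day maximum and the 14-day look-back.

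**Scale of one case.** At the planned 35 subjects per arm, one subject is 1/35 = 2.9 percentage points of that arm's remission rate. That is the most a single such case could remove, and only if the subject would otherwise have been in remission.

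**The case against.** The case against giving this much weight is strong in several respects.

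- **Seven days is only a floor.** Sites have up to 35 days, and one extra day is enough under the base assumptions. A reader might infer that the plan makes Baseline data unobtainable. It does not: Section 5.3.1.1 asks for 7 diary days net of the excluded ones, and a site that follows it has ample time to obtain them.
- **The floor has a coherent use.** A video-recorded ileocolonoscopy from up to 15 days before Screening is acceptable, and a re-screened subject may keep an endoscopy up to 30 days old. If it was done at least 3 days before the Screening Visit, 7 days of Screening give 7 usable days. The protocol does make the pre-Screening route conditional, including approval by the study designated physician.
- **Eligibility is a gate.** Inclusion 3 and 4 must be checked at Screening and Baseline and met before randomisation, and entry without meeting them is a reportable deviation. Most subjects without valid scores should therefore be kept in Screening or screen-failed.
- **Timing arguments cut both ways.** Central confirmation of SES-CD makes an endoscopy 1 or 2 days before Baseline unlikely. It also makes a 7-day Screening containing the endoscopy hard to complete. No turnaround times are given, so neither inference can be pressed.

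These points limit how often the problem can arise, but they do not close the gap. Inclusion 3 and 4 name no minimum number of usable days. The CDAI worksheet in Appendix D sums seven days, and Section 5.3.1.1 does not tell a site what to do with fewer; pro-rating appears only in the SAPs. The protocol's own 4-day minimum sits in the statistical text and is illustrated with post-Baseline visits. A site could enrol on a 3-day score that the analysis then rejects.

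A reader might also infer that precision at Baseline falls by a factor of 7/3 in the variance. That does not apply, because a 3-day score is set to missing rather than averaged. Averages of 4 to 6 days are expressly allowed and are not an error.

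**Conclusion.** The point holds in a limited form and is best labelled a cheap improvement. At the 7-day minimum, with the endoscopy 3 to 6 days before Baseline, 3 usable diary days remain where 4 are needed, and nothing in the plan prevents randomisation on them. The day count rests on one preparation day and a first entry on the Screening day. Other choices for these two assumptions leave the same or fewer usable days.

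The further step, from missing Baseline to a failure on clinical remission, is a reading of the general rules. The SAP has no specific rule for missing Baseline SF or AP, but NRI covers binary endpoints that are missing for any reason. The SAP's definition of Baseline as the last non-missing value up to first dose offers no evident fallback, since the diary starts only at the Screening Visit.

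A reader may want a count of affected subjects. The documents do not support one. They give neither the distribution of Screening lengths, nor the share of endoscopies done before Screening, nor the dates of endoscopy relative to Baseline.

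**What to change.** In Table 1, footnote a, and in the CDAI part of Section 5.3.1.1, add that a subject must have at least 4 usable diary days, preferably 7, before randomisation, after removing the preparation and endoscopy days. Have the e-diary or IRT check this at the Baseline Visit. Add a note for sites that, with an endoscopy inside Screening, this takes at least 8 days, and 11 days for a full 7 usable days, assuming one preparation day and a first entry on the Screening day. Keep the 35-day maximum.

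A compulsory 11-day minimum is not needed. The plan accepts averages over 4 days, and subjects whose endoscopy was at least 3 days before Screening lose no diary days.

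The cost is a sentence in two places, one system check, and a few more Screening days for the fastest subjects.
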